9.5 Treatment Compliance

Subject compliance in the Double-blind treatment and Follow-up periods will be evaluated by unused and used vial counts. Subjects will be asked to return all unused and empty vials at the next clinic visit. Vials will be visually inspected for opening. The number of unused and empty vials will be counted upon return and recorded in the drug accountability log kept at the site. To verify correct treatment in the Double-blind period the subjects will apply the tear-off label from the weekly kit in the Diary Card (see Section 10.4.2).

9.6 Drug Accountability

It is the responsibility of the investigator or trained designee to determine investigational drug accountability and complete the drug accountability log. Drug accountability will be reviewed by the monitor during monitoring visits and at the completion of the trial.

Unused IMP must be returned to supply vendor, or sent for destruction after agreement with the Sponsor, but only after the trial and overall drug accountability has been completed. A list of trial drug, used, or returned must be prepared and signed by the investigator or designee; an account must be given for any discrepancies.

Copies of all Drug Receipt Confirmations, Returned Clinical Supplies Reconciliation Forms and Drug Accountability Logs will be retained in the trial file. These forms are subject to regulatory inspection at any time.

9.7 Post-Trial Treatment

After completion of the trial, subjects who require further treatment will be offered treatment with molgramostim in in a Compassionate Use Programme, where national regulations so allow.

10 TRIAL ASSESSMENTS

10.1 Efficacy Assessments

10.1.1 Blood Gas Analysis

The following variables will be assessed from an arterial blood gas sample at the timepoints shown in *Table 1*:

- (A-a)DO₂ (mmHg/kPa)
- PaO₂ (mmHg/kPa)
- PaCO₂ (mmHg/kPa)

Sites that are experienced in the use of capillary sampling for blood gas analysis as part of their standard care, may use this option instead of an arterial blood gas sample at Screening (Visit 1), Weeks 4 and 12 (Visits 3 and 5) and all Follow-up Visits, but an arterial sample for blood gas is mandatory at Baseline (Visit 2) and Week 24 (Visit 8).

Subjects should rest for at least 10 minutes before puncture and the sample should be taken in supine position. Trial specific instructions will be provided in a separate document. The sample will be analysed in accordance with local routines.

If possible, arterial blood gases at Baseline should be conducted with the subject breathing room air. If the subject cannot tolerate temporary discontinuation of supplemental oxygen during blood gas sampling at Baseline, blood gas sampling at subsequent visits should be conducted using the same oxygen flow rate as was used at Baseline.

The (A-a)DO₂ will be calculated based on PaO₂, PaCO₂ and the ambient atmospheric pressure based on a standard equation (see section 10.2.1).

10.1.2 Lung Function Tests

The following lung function variables will be assessed at the timepoints shown in *Table 1*:

- VC (% predicted)
- DLCO (% predicted)
- FEV₁ (% predicted)
- FVC (% predicted)

VC, DLCO, FEV₁ and FVC will be assessed in accordance with the American Thoracic Society/European Respiratory Society (ATS/ERS) Task Force: Standardisation of lung function testing [36] by laboratory personnel with documented training in lung function testing. DLCO will be adjusted for haemoglobin value. VC, FEV₁ and FVC during the Double-blind period will be assessed using equipment provided by the Sponsor and centrally read. The VC (% predicted), FEV₁ (% predicted) and FVC (% predicted) for the DB period will be calculated based on a known standard.

VC, FEV₁ and FVC in the Follow-up period and DLCO will be assessed using local, appropriately calibrated equipment.

Trial specific instructions will be provided in a separate document.

10.1.3 Tolerance to Exercise

Tolerance to exercise will be assessed at the timepoints shown in *Table 1*:

- The 6MWT (Pre and Post walk dyspnoea score using the BDS, Blood oxygen saturation (SpO₂) (%) at start, Worst SpO₂ (%) during the walk, Distance walked (m), Duration of the walk (minutes and seconds), O₂ flow rate, reason for stopping early if applicable)

The 6MWT will be performed in accordance with ATS/ERS Task Force: Standardisation of lung function testing [36] by technicians with documented training and experience of performing the 6MWT in accordance with the referred ATS/ERS guidance. Trial specific instructions will be provided in a separate document.

If possible, the 6MWT should be conducted using room air. If the subject requires O₂ supplementation at rest, an O₂ titration procedure will be followed as part of the 6MWT at Screening in order to determine the amount of oxygen supplementation required for the subject to complete the test. The same flow of oxygen should then be used at the subject's subsequent tests in the trial, if possible.

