Subject Diary Card ^o		X	X	X	X	X	X	X		X	X ^q	X	X
Dispense trial drug		X	X	X	X	X	X	X		X	X ^q	X	
Compliance			X	X	X	X	X	X		X	X	X	X

- ^a Only related to anti-GM-CSF. Anti-GM-CSF blood sampling to be done during pre-screening period at trial sites that do not perform anti-GM-CSF as routine for aPAP diagnosis. Only subjects without available data will have a sample taken before screening to confirm diagnosis. Anti-GM-CSF blood sampling should be done only after collection of informed consent at such trial sites. Informed consent also to be taken in sites who conduct CT before screening.
- ^b Re-check of eligibility criteria.
- ^c Prior medication/therapy is defined as medication/therapy administered prior to first dose of trial medication. All medication/therapy administered after first dose of trial medication is considered concomitant medication/therapy.
- ^d Serum pregnancy test at Screening (Visit 1), at dosing at Baseline (Visit 2) and at all subsequent visits during trial. A urine pregnancy test will also be performed at dosing at Baseline (Visit 2) in order to immediately confirm that the subject is not pregnant and meets the inclusion criterion. Pregnancy tests (urine or serum) must continue at monthly intervals during treatment with inhaled molgramostim. Pregnancy tests at visit 10, 11, 12 and 13 for subjects who are not treated with inhaled molgramostim during the follow-up period are not mandatory.
- ^e Capillary sampling for blood gas analysis may be used instead of an arterial blood gas sample at Screening Visit 1, Visit 3, Visit 5 and all Follow-up Visits at sites that routinely use this method. Arterial sampling for blood gas is mandatory at Baseline (Visit 2) and Visit 8.
- ^f VC, DLCO, FEV₁, and FVC (all % predicted).
- ^g The need for supplemental O₂ during the procedure will be determined as part of the test at Screening or Baseline. The same O₂ flow will be used at the subsequent tests in the trial.
- ^h Haematology and clinical chemistry.
- ⁱ Samples for GM-CSF to be collected prior to 1st dose of trial drug and two hours after completion of administration of 1st dose of trial drug at Baseline (Visit 2) and prior to dosing and two hours after dosing at Week 4 (Visit 3).
- ^j Samples for anti-drug antibodies to be collected prior to administration of trial drug.
- ^k Biomarkers to be analysed: KL-6, CEA, Cyfra 21-1, SP-A, SP-B, SP-C, SP-D, and LDH.

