10.3.3.2 Oxygen Supplementation

Oxygen supplementation will be collected and recorded on the concomitant medication/therapy page of the eCRF throughout the trial for prior and concomitant supplementation.

Oxygen supplementation given only during assessments (according to *Section 10.1.1 or 10.1.3*) will not be recorded on the concomitant medication/therapy page, but under lung function and 6MWT pages, respectively.

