5.3.2 Definitions

Baseline	Baseline measurements refers to the last non-missing assessment made before randomisation. If a measurement is intended to be collected at the baseline visit, but is missing, then a corresponding measurement taken at the screening visit may be used to replace the missing assessment at the baseline visit.
Relative day	The relative day of an event is derived as follows: $\text{Relative day} = (\text{Start date}) - (\text{Date of first administration of IMP}) + 1.$ For days before the start date, calculate as $\text{Relative day} = (\text{Start date}) - (\text{Date of first administration of IMP})$. In this way, there will be no day=0. So, Day 1 is the same day as the day of first administration of IMP, and Day -1 is the day before.
(A-a)DO ₂	Alveolar-arterial oxygen difference is a measure of the difference between the alveolar concentration (A) of oxygen and the arterial (a) concentration of oxygen
DLCO	Uptake of carbon monoxide from a single inspiration in standard time.
FEV ₁	The volume of air that can forcibly be blown out in one second, after full inspiration.
FVC	The maximum amount of air a person can expel from the lungs after a maximal inhalation and during a forceful expiration.
SpO ₂	Indirect measurement of oxygen saturation using a finger probe, ear sensor or similar device.
6MWT	Test used to measure the distance that a subject can walk quickly on a flat hard surface in a period of 6 minutes (at an individually predetermined oxygen supplementation).
VC	The maximum amount of air a person can slowly expel from the lungs after a maximum slow inhalation.
% predicted	Calculation of % predicted of spirometry parameters collected during the double-blind period will be made centrally for statistical analysis using the same equation for all sites.
Region	For summaries and figures split by region 'Europe' will include: Denmark, France, Germany, Greece, Italy, Netherlands, Portugal, Russia, Slovakia, Spain, Switzerland and United Kingdom. 'Other' will include: Australia, Israel, South Korea and Turkey while Japan and the United States will be defined as their own regions.

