- Number of subjects with >10 percentage points improvement in FEV₁ (% predicted) after 24-weeks treatment
- Number of subjects with >10 percentage points improvement in FVC (% predicted) after 24-weeks treatment
- Number of subjects with >10% relative improvement in PaO₂ after 24-weeks treatment
- Number of subjects with improved tolerance to exercise (increase in distance walked ≥50 m or desaturation <4 percentage points on the 6MWT) compared to baseline after 24-weeks treatment
- Number of subjects with improved CT score after 24-weeks treatment

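### The protocol gives two rules for oxygen flow in the six-minute walk test, and neither the 6MWD analyses nor the desaturation category takes account of a changed flow

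*Protocol*

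**What the plan says.** **Which flow to use.** Protocol 10.1.3 (Tolerance to Exercise): "The same flow of oxygen should then be used at the subject's subsequent tests in the trial, if possible". Footnote g to Table 1 in Protocol 7.2.2: "The same O₂ flow will be used at the subsequent tests in the trial".

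**When the flow is set.** Footnote g: "The need for supplemental O₂ during the procedure will be determined as part of the test at Screening or Baseline". Protocol 10.1.3 describes titration for subjects who need oxygen at rest, and places it at one visit: "an O₂ titration procedure will be followed as part of the 6MWT at Screening". It does not cover a subject who starts on room air and later needs oxygen.

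**What the analysis assumes.** SAP 5.3.2 defines the test as one done "at an individually predetermined oxygen supplementation"; Protocol 3.2 defines it the same way.

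**What is recorded.** Protocol 10.1.3 lists oxygen flow rate among the 6MWT items. Under Protocol 10.3.3.2, oxygen given only for an assessment "will not be recorded on the concomitant medication/therapy page, but under lung function and 6MWT pages, respectively".

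**How the data are used.** SAP 5.3.7 analyses 6MWD with the primary-endpoint ANCOVA: treatment, WLL stratum, Japan versus other countries, and the baseline value. Its sensitivity analyses are limited to MMRM, multiple imputation, completers and the per-protocol set. The exercise-tolerance category is met by a gain of at least 50 m or by "desaturation <4 percentage points on the 6MWT) compared to baseline after 24-weeks treatment". Neither limb mentions flow.

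**The concern.** Walk distance and walk desaturation are both measured under whatever oxygen the subject is given. A change from Baseline is easy to interpret only if the flow is the same at both tests. One protocol passage guarantees that and the other does not, while the SAP definition presumes it.

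If flow does change, the report as planned has no analysis that would show whether it mattered. 6MWD is a confirmatory key secondary endpoint, and it set the sample size: SAP Appendix 2 takes 43 per group from it, and the sponsor then chose 45 per group, 135 in all. For the desaturation category the consequence is more direct. Extra oxygen at Week 24 can hold desaturation under 4 percentage points, and the subject is then scored as having improved exercise tolerance.

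**Working it through.** **1. Does any planned analysis deal with a changed flow?**

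- 6MWD ANCOVA and MMRM: no flow term (SAP 5.3.6, 5.3.7).
- Multiple imputation: fills in missing values only. A test done at a different flow is not missing.
- Completers: defined by finishing 24 weeks without stopping treatment.
- Per-protocol set (SAP 4): no flow criterion. Under the wording of Protocol 10.1.3 a changed flow need not be a deviation.
- Re-imputation after rescue (SAP 5.3.6): for (A-a)DO₂ only, and only after WLL, open-label molgramostim or rituximab.
- Oxygen-need regression (SAP 5.3.8): uses concomitant-therapy records, which exclude oxygen given only during a test.
- Descriptive output: SAP 5.3.7 says each 6MWT item will be summarised by visit. Flow is not among the items then named, nor in the title of Table 14.2.3.31. SAP Appendix 3 has a unit conversion for it.

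By contrast, the (A-a)DO₂ equation contains the inspired oxygen fraction. For subjects who need oxygen during sampling at Baseline, Protocol 10.1.1 asks for the Baseline flow at later visits without a feasibility exception.

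**2. Reproduce the plan's own figure (SAP Appendix 2, 6MWD).**

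Inputs: difference 50 m, residual MSE 4928.203, two-sided 0.05, power 90%. SD = √4928.203 = 70.2 m.

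Normal approximation: n = 2 × 4928.203 × (1.960 + 1.282)² / 50² ≈ 41.4, so 42 per group. The two-sample t-test gives 43, as stated. All six cells of the appendix table reproduce with the t-test (27, 32, 39 at 80% power; 35, 43, 52 at 90%). With the planned 45 per group, power at 50 m is 91.6%.

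**3. Illustrate the effect of a flow imbalance.**

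Let f be the excess share of subjects in one arm tested at a higher flow at Week 24, and g the metres gained by each. The between-arm difference moves by f × g. Neither f nor g is in the documents; the values below are assumptions. The table puts the excess in the placebo arm, with a true difference of 50 m, SD 70.2 and 45 per group.

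| f | g (m) | shift (m) | difference left (m) | power, two-sided 0.05 |
|---|---|---|---|---|
| – | – | 0 | 50 | 91.6% |
| 5% | 20 | 1 | 49 | 90.6% |
| 10% | 30 | 3 | 47 | 88.1% |
| 10% | 40 | 4 | 46 | 86.7% |
| 20% | 40 | 8 | 42 | 80.1% |
| 20% | 50 | 10 | 40 | 76.2% |

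At 0.0167, the smallest of the truncated Hochberg levels in SAP 5.4, power is 82.4% with no shift, 74.7% after a 4 m shift and 65.5% after 8 m. After a 4 m shift, 90% power at 0.05 would need 50 per group.

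If the excess is in the active arm, the same f × g is added to the observed difference instead.

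**The case against.** **The direction is not established.** A reader might infer that added oxygen goes mainly to deteriorating placebo subjects, so that the bias is towards no effect. The documents do not support that. They give no flow data by arm, and Protocol 5.3 names bronchoconstriction, dyspnoea and decreased pulmonary function as potential drug effects, so extra oxygen on active treatment is also conceivable. This objection stands.

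**The metres are assumed.** A reader might take the table as an estimate of lost power. It is not one. The only deterioration figure in the documents is 4 WLL events among 78 randomised subjects (SAP Appendix 2). Even if all four fell in a placebo third of about 26, that is 4/26 = 15%, so the larger values of f look high. Needing WLL is not the same as walking on more oxygen, and the appendix itself thinks the event rate slightly underestimated, so this is only a rough guide. The objection stands as to size.

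**Protocol 10.1.3 keeps constant flow as the default.** It allows a feasibility exception, not free choice, and it refers to ATS/ERS guidance and to separate trial instructions that are not in the documents. Those may limit exceptions. They do not remove the conflict between two protocol passages or supply an analysis rule.

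**Flow may already be summarised.** The statement that each 6MWT item will be summarised could cover it, and individual 6MWT data are listed. So it would be too strong to say that flow appears in no output. It is in no model, sensitivity analysis or responder rule.

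**The responder category is supportive.** It lies outside multiplicity control, and the main 6MWD analysis deliberately takes all observed data. A reader might infer that the confirmatory analysis is invalid. It is not: it estimates a de-facto effect that includes whatever oxygen was given. What is missing is a way to see how much of that effect depends on changed test conditions.

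**Conclusion.** The concern holds as a textual conflict and a gap in the SAP. Protocol 10.1.3 and footnote g differ on whether flow must stay constant and on when it is set. Recorded flow enters no 6MWD inferential or sensitivity analysis. The desaturation category can score a subject on more oxygen than at Baseline as improved. These points follow from the text and need no assumption.

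The frequency, arm and size of flow changes cannot be known from the documents, so neither the sign nor the amount of any bias in 6MWD can be stated. The fall from 91.6% to 86.7% for a 4 m shift shows sensitivity only. It assumes a 10% excess in placebo gaining 40 m each, a true difference of 50 m, SD 70.2 m and complete data on 45 per arm. No stated sample-size figure is wrong. This is a cheap improvement, not a threat to the confirmatory result.

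**What to change.** 1. Reconcile Protocol 10.1.3 with footnote g, on constancy of flow and on the visit and subjects for which it is set. Which rule applies is for the sponsor to state.
2. In SAP 5.3.7 keep the all-data ANCOVA as the main 6MWD analysis, so type I error control and the de-facto approach do not change.
3. Add one supportive 6MWD analysis: set to missing any Week 24 test done at a flow different from Baseline, higher or lower, and impute with the multiple imputation method already in SAP 5.3.6. Optionally add a shift towards worse values for tests at a higher flow.
4. In the desaturation category, do not count as improved a subject tested at a higher flow than at Baseline.
5. Name oxygen flow in the 6MWT summary: number of tests at lower, same and higher flow than Baseline, by arm and visit.

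These rules should be fixed before unblinding. The cost is a small wording change in protocol and SAP, one table and one further supportive analysis to report. The data are already collected on the 6MWT page.

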10.1.4 Dyspnoea Score

The Dyspnoea score will be assessed at the timepoints shown in *Table 1*.

Dyspnoea severity will be established using the Borg CR10 Scale (BDS - *Appendix C*). The BDS will be used before the 6MWT and immediately after the 6MWT. Questionnaires in the local language will be used.

10.1.5 Cough Scores

Subjects will be asked to score the severity and frequency of coughs on a visual analogue scale (Cough Questions - CQ - *Appendix D*) at the timepoints shown in *Table 1*. Questions will be in the local language.

10.1.6 CT Scoring

High Resolution CT scans will be performed at the timepoints shown in *Table 1* according to a trial-specific image acquisition protocol.

A trial specific instruction describing the handling, transferring, blinding, distribution, assessment, result processing, and filing of data will be provided to all concerned personnel.

Two independent and blinded assessors will examine the scans. The assessments will be performed centrally on a per subject basis; the Baseline (Visit 2) and Week 24 (Visit 8) scans will be assessed at the same time for the individual subjects. The extent of ground-glass opacification in the CT scans will be quantified visually, as previously described [18].

The improvement will be graded as: Improved / Worsened / No change / Data missing – Impossible to evaluate.

The CT scans will also be evaluated for safety and any detrimental effects of treatment detected at Week 24 (Visit 8) will be recorded as AEs.

Further the CT scans will be evaluated using quantitative assessment at a sufficiently qualified laboratory.

10.1.7 Quality of Life Score

Subjects will be asked to assess their QoL at the timepoints shown in *Table 1*.

Subjects will be asked to complete the following questionnaires:

- The St Georges Respiratory Questionnaire (SGRQ) is a respiratory specific questionnaire which is available in the local language. The symptoms component with 3-month symptoms recall will be used, *Appendix A*. This disease-specific instrument

has been designed to measure impact on QoL in subjects with obstructive airway disease. This assessment is considered relevant for use in subject population of this trial.

- The EuroQol-5D (EQ-5D) is a more general questionnaire which is widely used to measure health outcome in terms of mobility, self care, usual activities, pain/discomfort, anxiety/depression. The 5 level instrument (EQ-5D-5L) which uses a 5-point scale (no problems, slight problems, moderate problems, severe problems, and extreme problems) will be used in the local language, *Appendix B*. This instrument will be used to measure overall self-rated health status.

10.1.8 Disease Severity Score

The DSS will be assessed at the timepoints shown in *Table 1*.

The DSS is based on the presence of symptoms and degree of reduction in PaO₂ determined with the individual breathing room air in the supine position [37].

The DSS is a 5-point score as follows:

- 1 = no symptoms and PaO₂ ≥ 70 mmHg
- 2 = symptomatic and PaO₂ ≥ 70 mmHg
- 3 = 60 mmHg ≤ PaO₂ < 70 mmHg
- 4 = 50 mmHg ≤ PaO₂ < 60 mmHg
- 5 = PaO₂ < 50 mmHg.

If possible, the blood gas assessment should be conducted with the subject breathing room air (see 10.1.1). For subjects requiring supplemental oxygen during the blood gas assessment the DSS will be based on the PaO₂ obtained while breathing oxygen.

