10.2.3 Exploratory Endpoints

10.2.3.1 Double-Blind Treatment Period

- Absolute change from baseline of (A-a)DO₂, VC (% predicted), DLCO (% predicted), FEV₁ (% predicted), FVC (% predicted), and relative change from baseline of PaO₂ after 4 and 12-weeks, treatment
- Time period during which the (A-a)DO₂ level is maintained below Baseline –10mmHg
- Number of subjects with improved tolerance to exercise (increase in distance walked ≥ 50 m or desaturation <4 percentage points on the 6MWT) after 4 and 12-weeks treatment
- Time period during which the improvement in tolerance to exercise is maintained
- Change from baseline in dyspnoea score and cough scores after 4 and 12-weeks treatment
- Number of subjects with improved QoL (change of ≥4 units on the SGRQ/number of subjects with 'no problems' in the EQ-5D-5L), after 4, 12, and 24-weeks treatment
- Change in serum concentration of biomarkers; KL-6, CEA, SP-A, SP-B, SP-C, SP-D, Cyfra 21-1 and LDH after 4, 12, and 24-weeks treatment
- Levels of anti-GM-CSF after 4, 12 and 24-weeks treatment
- Change in serum concentration of GM-CSF post first dose of trial drug and after 4-weeks treatment
- Number of subjects in need for oxygen supplement therapy during 24-weeks treatment
- The distribution of DSS at Screening and at Week 24
- The percentage of subjects with DSS 1 or 2 at Week 24

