- Number of subjects with improved QoL (reduction of ≥4 units on the SGRQ) after 4, 12, and 24-weeks treatment
- Number of subjects with 'no problems' in EQ-5D-5L after 4, 12, and 24-weeks treatment
- Change from baseline in serum concentration of biomarkers: Krebs von den Lungen-6 (KL-6), Carcinoembryonic antigen (CEA), Surfactant Protein A (SP-A), Surfactant

Protein B (SP-B), Surfactant Protein C (SP-C), Surfactant Protein D (SP-D), Cytokeratin 19 Fragment (Cyfra 21-1) and Lactate Dehydrogenase (LDH) after 4, 12, and 24-weeks treatment

- Anti Granulocyte Macrophage Colony Stimulating Factor (GM-CSF) antibody titers after 4, 12 and 24-weeks treatment
- Change in serum concentration of GM-CSF post first dose of trial drug and after 4-weeks of treatment
- Number of subjects in need for oxygen supplement therapy during 24-weeks treatment.
- The distribution of DSS at Screening and at Week 24
- The percentage of subjects with DSS 1 or 2 at Screening and at Week 24.

Follow-up period

- Number of subjects requiring WLL or other treatment for aPAP and number of treatment courses required during 48-weeks follow-up.
- Time to WLL, or other treatment for aPAP during 48-weeks follow-up.
- Absolute change from baseline in (A-a)DO₂ and VC (% predicted), DLCO (% predicted), FEV₁(% predicted) , FVC (% predicted), and and relative change from baseline of PaO₂ after 12, 24, 36 and 48-weeks follow-up
- Number of subjects with improved tolerance to exercise (increase in distance walked ≥50 m or desaturation <4 percentage points on the 6MWT) after 12, 24, 36 and 48-weeks follow-up
- Number of AEs, severe AEs, SAEs and ADRs , including clinically significant changes in laboratory tests and ECG variables, during 48-weeks follow-up
- Levels of anti-GM-CSF after 12 and 24 weeks follow-up.
- The distribution of DSS after 24 and 48-weeks follow-up
- The percentage of subjects with DSS 1 or 2 after 24 and 48-weeks follow-up.

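### DSS is defined on room air but scored on supplemented PaO₂ for subjects who need oxygen, so a subject moving from air to oxygen by Week 24 can be tabulated as improved despite worsening

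*Protocol*

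**What the plan says.** Protocol 10.1.8 bases the DSS on symptoms and on PaO₂ "determined with the individual breathing room air in the supine position". DSS 1 and 2 share one oxygen threshold and differ only in symptoms ("2 = symptomatic and PaO₂ ≥ 70 mmHg"). DSS 3, 4 and 5 follow at 60 to below 70, 50 to below 60, and below 50 mmHg.

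The section then relaxes the room-air condition: "If possible, the blood gas assessment should be conducted with the subject breathing room air". Where that is not possible, "For subjects requiring supplemental oxygen during the blood gas assessment the DSS will be based on the" PaO₂ on oxygen. It makes no adjustment for FiO₂ and sets no separate category.

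Protocol 10.1.1 contains the one safeguard. "If the subject cannot tolerate temporary discontinuation of supplemental oxygen during blood gas sampling at Baseline", then "blood gas sampling at subsequent visits should be conducted using the same oxygen flow rate as was used at Baseline".

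Two exploratory endpoints use the score during double-blind treatment: its distribution and the proportion in the two mildest grades. The second is "The percentage of subjects with DSS 1 or 2 at Week 24" in Protocol 10.2.3.1 and "The percentage of subjects with DSS 1 or 2 at Screening and at Week 24" in SAP 2.2. SAP 5.3.8 produces shift tables of the observed scores and of DSS 1 or 2 against the rest, with no rule on oxygen. Both endpoints recur in the follow-up period. SAP 5.8, Table 2, also uses DSS 2, 3, 4 and 5 as the disease-severity subgroups.

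**The concern.** PaO₂ on supplemental oxygen is not on the same scale as PaO₂ on air, because raising FiO₂ raises alveolar oxygen directly. The primary endpoint allows for this, since FiO₂ is a term in the (A-a)DO₂ equation. The DSS does not.

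The exposed subject is sampled on air at Screening or Baseline and cannot be sampled on air at Week 24. The same-flow rule does not reach this subject, because no Baseline flow exists to repeat. Needing oxygen for sampling is a sign of deterioration, yet the supplemented value is read against the room-air cut-offs and may fall in DSS 1 or 2. A reader of the shift table could not tell recovery from the start of oxygen.

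A second, separate route concerns severity at entry. A subject already sampled on oxygen when the DSS is first scored can be placed in a mild severity subgroup despite severe disease.

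**Working it through.** The documents give no figure for this effect, so the check applies the protocol's own gas equation to the DSS cut-offs.

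**Inputs from the documents:** water vapour pressure 47 mmHg and divisor 0.8 (Protocol 10.2.1; SAP 5.3.6); cut-offs 70, 60 and 50 mmHg (Protocol 10.1.8).

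**Assumptions not in the documents:** atmospheric pressure 760 mmHg; PaCO₂ 40 mmHg; FiO₂ 0.24 or 0.28 on oxygen; room-air gradient 45 mmHg at Week 24; gradient on oxygen unchanged, 25% wider (56.25) or 50% wider (67.5).

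**Formula:** PaO₂ = FiO₂ × (760 − 47) − 40/0.8 − gradient.

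**Step 1: alveolar oxygen, before subtracting the gradient**
- Air: 0.21 × 713 − 50 = 99.7
- FiO₂ 0.24: 0.24 × 713 − 50 = 121.1
- FiO₂ 0.28: 0.28 × 713 − 50 = 149.6

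**Step 2: largest gradient that still gives PaO₂ of at least 70 (DSS 1 or 2)**
- Air: 99.7 − 70 = 29.7
- FiO₂ 0.24: 121.1 − 70 = 51.1
- FiO₂ 0.28: 149.6 − 70 = 79.6

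**Step 3: a subject who worsens**

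At Screening on air, PaO₂ is 65, so the gradient is 99.7 − 65 = 34.7 and the DSS is 3. By Week 24 the gradient on air would be 45, giving PaO₂ 99.7 − 45 = 54.7 and DSS 4. If sampled on oxygen instead:

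| Gradient on oxygen | FiO₂ 0.24 | FiO₂ 0.28 |
|---|---|---|
| 45 (unchanged) | 121.1 − 45 = 76.1, DSS 1/2 | 149.6 − 45 = 104.6, DSS 1/2 |
| 56.25 (25% wider) | 121.1 − 56.25 = 64.9, DSS 3 | 149.6 − 56.25 = 93.4, DSS 1/2 |
| 67.5 (50% wider) | 121.1 − 67.5 = 53.6, DSS 4 | 149.6 − 67.5 = 82.1, DSS 1/2 |

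A true move from DSS 3 to DSS 4 is tabulated as improvement in four of the six cells, as no change in one, and correctly in one. At FiO₂ 0.24 the false improvement disappears once the gradient is more than about 14% wider (51.1/45 = 1.14). At 0.28 it persists until about 77% wider (79.6/45 = 1.77).

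**Step 4: can DSS 1 occur at entry?**

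Protocol 8.2 has no symptom criterion. It requires a gradient of at least 25 mmHg, with either resting PaO₂ below 75 or exercise desaturation. Under the same assumptions, room-air PaO₂ can be at most 99.7 − 25 = 74.7. An asymptomatic subject between 70 and 74.7 is therefore eligible and is DSS 1, but Table 2 of SAP 5.8 has no such stratum.

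**The case against.** The strongest reply is that this is an open operational rule: the section gives the definition, asks for room air where possible and then states the exception. Moreover, Protocol 10.1.1 holds the flow constant for subjects who cannot come off oxygen at Baseline, which largely standardises their within-subject change, and it treats temporary discontinuation for sampling as the preferred course. All of that stands. It narrows the exposed group to subjects sampled on air early who cannot be sampled on air at Week 24, but it does not give a rule for them.

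The low consequence also stands. SAP 5.3.8 treats exploratory endpoints descriptively, and DSS lies outside the testing procedure of SAP 5.4. Oxygen use has its own logistic regression in SAP 5.3.8. That analysis is not linked to DSS, however, and oxygen given only during assessments is not recorded on the page it draws on (Protocol 10.3.3.2).

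A reader might infer several stronger things that the documents do not support:
- **That the most severe subjects are graded mild as a matter of course.** They can be. With FiO₂ 0.24 and a 50% wider gradient the grade is unchanged.
- **That becoming oxygen-dependent is enough.** The score changes only if the blood gas sample itself is taken on oxygen.
- **That such a subject becomes DSS 1.** A newly oxygen-dependent subject would probably be symptomatic, hence DSS 2. The summary pools the two grades.
- **That new oxygen need at Week 24 distorts the severity subgroups.** Taking these as fixed at entry, which Table 2 does not state but is the natural reading, only oxygen use at entry can misplace a subject.
- **That the error favours molgramostim.** If more placebo subjects start oxygen, it would flatter placebo.

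**Conclusion.** The concern holds in a limited form. The definition and the scoring exception in Protocol 10.1.8 put different quantities on one scale, the same-flow rule does not cover a move from air to oxygen, and the SAP adds nothing. Such a subject can be shown as improved while worsening. Under the assumed pressures and a room-air gradient of 45 mmHg, this happens at FiO₂ 0.28 for any widening up to 50%, and at FiO₂ 0.24 only if the gradient widens little.

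The documents give no count of affected subjects, so neither the size nor the direction of any bias between arms can be computed; the number could be very small or zero. The point touches the exploratory DSS summaries and, through oxygen use at entry, the descriptive severity subgroups. It does not affect the primary or key secondary tests. It is a minor point, worth correcting because the correction is cheap.

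**What to change.** Amend the SAP before unblinding. The changes concern tabulation only and leave oxygen use and sampling as they are.

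1. Flag every DSS value obtained on oxygen. Show these values as a separate category in the shift tables, the DSS 1 or 2 summary and the severity subgroups.
2. Add a shift table and a DSS 1 or 2 percentage restricted to subjects sampled on room air at both visits.
3. State that a subject who moves from room air to oxygen is not counted as improved.
4. Report subjects on the same oxygen flow at both visits separately. Forcing them to non-response would mean they could never respond, however much PaO₂ rose at fixed flow.
5. As a separate small point, label the lowest severity subgroup DSS 1–2, since the entry criteria do not exclude DSS 1.

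The cost is SAP wording and a few tables. FiO₂ is already needed to recalculate (A-a)DO₂ under SAP 5.3.6, so no new data are required. The downside is one extra category, which may be small.
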